4.3. Type and Number of Subjects

In Part 1, up to 16 subjects with normal renal function will be matched to approximately 8 subjects with moderate renal impairment, and approximately 8 subjects with severe renal impairment and/or subjects with ESRD not on hemodialysis for a total of approximately 32 subjects. In Part 2 (optional), approximately 4 to 8 subjects with normal renal function (if enrolled), approximately 4 to 8 subjects with mild renal impairment, and approximately 4 to 8 subjects with ESRD on hemodialysis will be enrolled for a total of approximately 12 to 24 subjects.

If there are a sufficient number of subjects with normal renal function enrolled in Part 1 (Group A) that match subjects with renal impairment in other groups, a determination will be made regarding enrollment of matching subjects with normal renal function in Part 2 (Group D). In addition, if subjects prematurely discontinue the study, additional replacement subjects may be enrolled at the discretion of the Sponsor in consultation with the investigator.

4.4. Design Justification

This study design is commonly used when evaluating the pharmacokinetics of a drug entity in subjects with impaired renal function. It is based on recommendations given in the FDA draft guidance for industry, Pharmacokinetics in Patients with Impaired Renal Function — Study Design, Data Analysis, and Impact on Dosing and Labeling [DHHS, 2010].

Gepotidacin exhibits linear and time-independent pharmacokinetics, which indicates a single-dose study is adequate to achieve study objectives. A multiple-dose study is not necessary since there are no safety concerns with metabolites of this study drug.

4.5. Dose Justification

The proposed single IV infusion dose of gepotidacin 750 mg administered over 2 hours will provide an approximate 2.5-fold margin for mean C_{max} and AUC based on the highest single IV dose of gepotidacin (1800 mg) evaluated in adult healthy subjects.

A physiologically-based pharmacokinetic (PBPK) model was developed for gepotidacin using the SimCYP population based absorption, distribution, metabolism, and excretion (ADME) simulator Version 15 (Certara USA, Inc, Princeton, NJ). Pharmacokinetic data from healthy Caucasian subjects following single 2-hour IV infusion doses of 400 mg, 1000 mg, and 1800 mg (see GSK Document Number 2014N198291_00 Study ID BTZ115198) was used to predict the intrinsic hepatic clearance. The predictive performance of the PBPK model was verified by comparing the observed AUC from time 0 to the time of the last quantifiable concentration (AUC(0-t)) and C_{max} of gepotidacin to the predicted values at the 3 doses of 400 mg, 1000 mg, and 1800 mg. This model was further validated using a 750-mg IV 2-hour infusion dosing regimen in Japanese subjects from the same clinical study [see report of Study BTZ115198]. The model predictions agreed well with the observed data for the Caucasian population for all 3 dosing regimens, with predicted and observed values of a 5% to 12% difference in AUC(0-t) and a 1% to 5% difference, respectively, in C_{max}. Simulations were also in good agreement with PK data in Japanese subjects. The model input parameters are listed in [Appendix 11](#).

The PBPK model was then utilized to predict exposure for the proposed dosing regimen (750-mg IV 2-hour infusion) in healthy Caucasian subjects with normal renal function and subjects with various levels of impaired renal function as implemented in SimCYP with a female to male ratio of 0.5. The simulations were performed with the assumption of only GFR changes in subjects with renal impairment (software “RenalGFR30-60” and “RenalGFR_less_30”) and no active renal secretion due to the limited understanding of renal uptake mechanism for gepotidacin. The predicted geometric mean in gepotidacin exposure (AUC(0-t)) for subjects with moderate and severe renal impairment was

increased up to 2.0-fold compared with healthy subjects with normal renal function (Table 1).

Table 1 Simulated Gepotidacin Pharmacokinetic Parameters in Healthy (Normal) and Renally Impaired Populations

Pharmacokinetic Parameters	Predicted Geomean (CV%) [N = 100]		
	Healthy (Normal Renal Function) (GFR ≥90 mL/min)	Moderate Renal Impairment (GFR 30 to 60 mL/min)	Severe Renal Impairment (GFR 15 to <30 mL/min)
C _{max} (µg/mL)	5.65 (18)	7.29 (19)	7.93 (20)
AUC(0-t) (µg•h/mL)	17.5 (23)	25.8 (24)	28.9 (26)

CV = coefficient of variation; GFR = glomerular filtration rate; N = number of subjects included in the simulation

4.6. Benefit:Risk Assessment

Summaries of findings from both clinical and nonclinical studies conducted with gepotidacin can be found in the Investigator's Brochure (IB). The following section outlines the risk assessment and mitigation strategy for this protocol.

4.6.1. Risk Assessment

Potential Risk of Clinical Significance	Summary of Data/Rationale for Risk	Mitigation Strategy
Investigational Product (IP) Gepotidacin		
Gastrointestinal (GI) Effects	
Lower GI effects (soft stools, flatulence, and diarrhoea) are the most common GI-associated adverse events (AEs) reported in human subjects dosed with gepotidacin.
 
In the Phase I studies, out of approximately 400 healthy subjects who have received gepotidacin, C. difficile has been reported in 8 subjects.
	
Exclusion criterion and close monitoring of clinical parameters and AEs will be conducted to mitigate and assess GI effects.
 
Patients with significant GI symptoms will obtain the appropriate work-up (Appendix 8).
 
Subject stopping criteria: Subjects experiencing Grade 3 or Grade 4 AEs will have permanent discontinuation of the investigational medication and will be followed as appropriate until resolution of the AE.

Cardiovascular Effects Reversible increase in QT prolongation and a mild increase in heart rate in human subjects.	In Study BTZ115775 [see GlaxoSmithKline Document Number 2015N227098_00 Study ID BTZ115775], the infusion of gepotidacin at a dose of 1000 mg and 1800 mg over 2 hours caused a mild heart rate effect of approximately 6 bpm to 10 bpm and a QT prolongation, measured as $\Delta\Delta\text{QTcF}$, of 12 msec to 22 msec. The QT prolongation evolved during the infusion and was quickly reversed over 2 hours after the end of the infusion. Blood pressure observations were within normal ranges.	
Exclusion criteria, close monitoring of clinical parameters, and AEs will be conducted and stopping criteria will be utilized to mitigate and assess cardiovascular effects.
 
Note: Subjects with a QRS duration <70 and >120 msec will be excluded.
 
Subject stopping criteria: Subjects experiencing a QTcB and/or QTcF >500 msec and/or a change from baseline in QTc >60 msec.

Acetylcholinesterase (AChE) Inhibition In a mass spectrometry model performed with gepotidacin, AChE was inhibited with a concentration of inhibitor where the response (or binding) was reduced by half (inhibitory concentration) of approximately 5 µg/mL (7.5 µg/mL of total drug concentration).	At higher doses, some subjects have experienced effects consistent with increased cholinergic tone, including central nervous system and GI effects (increased salivation, slurred speech, blurred vision, dizziness, light-headedness, and GI upset). These effects appear to be related to C _{max} and are significantly attenuated when C _{max} is below 14 µg/mL.	
Coadministration of anticholinergics and administration in subjects with certain concomitant conditions will be excluded.
 
Close monitoring of clinical parameters and AEs will be conducted to assess effects potentially related to AChE inhibition. The C_{max} will be below 14 µg/mL in this study.

Potential Risk of Clinical Significance	Summary of Data/Rationale for Risk	Mitigation Strategy
Infusion-Site Reactions	
Infusion-site reactions (mild to moderate), including phlebotrombosis, have been observed more frequently following repeat dosing at higher doses (≥ 750 mg BID).
 
Infusion-site reaction events were reported as AEs for 2 of 122 subjects (2%) and consisted of mild, related infusion-site pain (see GSK Document Number 2015N243789_00 Study ID BTZ116704).
	
Intravenous administration of gepotidacin is given by a slow infusion following carefully defined procedures to minimize risk of infusion site reactions.
 
Infusion-site reactions will be evaluated in an ongoing fashion throughout the study with interventions implemented as appropriate.

Rash/Hypersensitivity	
A fine, mild, generalized pruritic macular skin rash was seen in 3 of 8 subjects following 10 days of dosing 1500 mg 3 times daily (see the report of Study BTZ115198).
 
Rash was reported as an AE for 4 of 122 subjects (3%) and consisted of mild, related urticaria; moderate, related rash maculopapular; mild, related rash; mild, related urticaria; and mild, not related arthropod bite (see report of Study ID BTZ116704).
 
There has been no other evidence of hypersensitivity in human subjects to date.
	
Exclusion criterion: History of sensitivity to any of the study drugs, components thereof, or a history of drug or other allergy that, in the opinion of the investigator or GlaxoSmithKline medical monitor, contraindicates their participation.
 
Subject monitoring: Patients will be monitored closely for cutaneous effects throughout the study, and specialist advice will be sought as needed to evaluate any clinically significant finding.
 
Subject stopping criteria: Grade 3 or higher rash or Grade 2 rash with evidence of systemic involvement.

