In Part 2 (optional) of the study, subjects in Group F will participate in 2 treatment periods, with dosing in these periods separated by a washout period of at least 7 days. Subjects in Group F will enter the clinic at Check-in (Day -1, Period 1 and Day 7, Period 2) before each study drug administration (Day 1, Period 1 and Day 8, Period 2). On Day 1 (Period 1) and Day 8 (Period 2), subjects in Group F will receive a single dose of study drug as follows: gepotidacin 750 mg administered as a 2-hour IV infusion starting approximately 2 hours before the initiation of the last hemodialysis session of the week (Period 1) and gepotidacin 750 mg administered as a 2-hour IV infusion starting within 2 hours after completion of the last hemodialysis session of the week (Period 2). Subjects in Group F will be discharged from the clinic on Day 10 of Period 2 after all scheduled PK and safety assessments have been completed, and will return to the clinic for a Follow-up Visit approximately 10 days (± 5 days) after the last dose administration in Period 2. The duration of the study (from Screening to the Follow-up Visit) will be approximately 50 days.

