uses heparin to maintain IV cannula patency).

CONCOMITANT MEDICATIONS

12. Subject has used medications known to affect the elimination of serum creatinine (e.g., trimethoprim or cimetidine) or competitors of renal tubular secretion (e.g., probenecid) within 30 days before dosing.
13. Subjects cannot use any over-the-counter, or prescription medication (except for hormonal contraceptives and/or acetaminophen; see Section 6.11 for more details), vitamin supplement, or herbal medication within 7 days (or 5 half-lives, whichever is longer) before dosing and during the study within 7 days before dosing and during the study. Any exceptions (including subjects with renal impairment that will be on medications during the study) will be discussed with the sponsor or medical monitor on a case-by-case basis and the reasons will be documented.

DIAGNOSTIC ASSESSMENTS AND OTHER CRITERIA

14. Subjects with normal renal function have a presence of hepatitis B surface antigen or positive hepatitis C antibody test result at Screening or within 3 months prior to first dose of study treatment. A subject with renal impairment with stable hepatitis C who has normal liver function test results is allowed with investigator approval.
15. A positive test for human immunodeficiency virus antibody.
16. Subject has clinically significant abnormal findings in serum chemistry, hematology, or urinalysis results obtained at Screening or Day -1 (and Day 7 for Group F only), other than those associated with underlying renal conditions or other stable medical conditions consistent with the disease process.
17. Subject with normal renal function has a baseline corrected QT interval using the Fridericia formula (QTcF) of >450 milliseconds (msec) and subject with renal impairment has a baseline QTcF of >480 msec.

OTHER EXCLUSION CRITERIA

18. Donation of blood in excess of 500 mL within 12 weeks prior to dosing or participation in the study would result in donation of blood or blood products in excess of 500 mL within a 56 day period.
19. Previous exposure to gepotidacin within 12 months prior to the first dosing day.
20. The subject has participated in a clinical trial and has received an investigational product within the following time period prior to the first dosing day in the current study: 30 days, 5 half-lives, or twice the duration of the biological effect of the investigational product (whichever is longer).

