Saliva collection for pharmacokinetics ^c			X	X	X		See Table 3 for time points.
AE/SAE review	X	X	←-----→			X	
Concomitant medication review		X	←-----→			X	

AE = adverse event, Clcr = estimated creatinine clearance; eGFR = estimated glomerular filtration rate, ECG = electrocardiogram, FSH = follicle stimulating hormone; HIV = human immunodeficiency virus; PGx = pharmacogenetic, SAE = serious AE; WCBP = women of childbearing potential.

- a If test has otherwise been performed within 3 months before the first dose of study treatment, testing at Screening is not required.
- b Informed consent for optional substudies (e.g., genetics research) must be obtained before collecting a sample.
- c Subjects in Part 1 only. It should be noted that subjects with renal impairment may be on medications that may prevent saliva collections.

Table 3 Safety and PK Assessments (Groups A, B, C, D, and E)

Procedure ^a	Predose	Treatment Period Time point (hours)														
		0	0.25	0.5	1	1.5	2	2.5	3	4	6	8	12	24 ^b	36 ^b	48 ^b
12-lead electrocardiogram	X					X	X			X		X	X	X	X	X
Vital signs	X					X	X			X		X	X	X	X	X
Treatment administration 2-hour IV gepotidacin infusion		X														
Blood collection for pharmacokinetics	X		X	X	X	X	X	X	X	X	X	X	X	X	X	X
Urine collection for pharmacokinetics (subjects with normal renal function) ^c	X	X					X			X	X	X	X	X	X	
Urine collection for pharmacokinetics (subjects with renal impairment) ^d	X	X								X		X	X	X	X	
Saliva collections ^e	X		X	X	X	X	X	X	X	X	X	X	X	X	X	X

^a When coinciding with safety and/or pharmacokinetic assessments, electrocardiograms, vital signs, and pharmacokinetic blood collections should be performed in said order.

^b The 24-, 36-, and 48-hour postdose time points correspond to time points on Day 2 and 3, respectively.

^c Urine collection intervals for subjects with normal renal function (Group A and Group D) include 0 (pre-dose), 0 to 2 hours, 2 to 4 hours, 4 to 6 hours, 6 to 8 hours, 8 to 12 hours, 12 to 24 hours, 24 to 36 hours, and 36 to 48 hours.

^d Urine collection intervals for subjects with renal impairment (Group B, Group C, and Group E) include 0 hour (pre-dose), 0 to 6 hours, 6 to 12 hours, 12 to 24 hours, 24 to 36, and 36 to 48 hours.

^e Subjects in Part 1 only. It should be noted that subjects with renal impairment may be on medications that may prevent saliva collections.

Table 4 Time and Events Tables (Group F)

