Blood collection for pharmacokinetics			X	X	X			X	X	X			See Table 5 for time points.
Urine collection for pharmacokinetics			X	X	X			X	X	X			See Table 5 for time points. Subjects may not be able to produce a urine sample.
Dialysate collections for pharmacokinetics			X	X	X								See Table 5 for time points.
AE/SAE review	X	X	←=====→								X		
Concomitant medication review		X	←=====→					←=====→			X		

Footnotes continued on the next page.

AE = adverse event, eGFR = estimated glomerular filtration rate, ECG = electrocardiogram, FSH = follicle-stimulating hormone; HIV = human immunodeficiency virus, PGx = pharmacogenetic, SAE = serious AE; WCBP = women of childbearing potential.

- a For subjects on hemodialysis (Part 2 [optional], Group F), assessments performed on scheduled hemodialysis days are to be done before hemodialysis (except for PK sample collection, which will be done before and after hemodialysis).
- b Subjects in Group F will participate in 2 treatment periods, with dosing in these periods separated by a washout period of at least 7 days. Subjects in Group F will enter the clinic at Check-in (Day -1, Period 1 and Day 7, Period 2) before each study drug administration (Day 1, Period 1 and Day 8, Period 2). On Day 1 (Period 1) and Day 8 (Period 2), subjects in Group F will receive a single dose of study drug as follows: gepotidacin 750 mg administered as a 2-hour IV infusion starting approximately 2 hours before initiation of the last hemodialysis session of the week (Period 1) and gepotidacin 750 mg administered as a 2-hour IV infusion starting within 2 hours after completion of the last hemodialysis session of the week (Period 2). Subjects in Group F will be discharged from the clinic on Day 10, Period 2.
- c If test has otherwise been performed within 3 months prior to first dose of study treatment, testing at Screening is not required.
- d Informed consent for optional substudies (e.g., genetics research) must be obtained before collecting a sample.

Table 5 Safety and Pharmacokinetic Assessments (Group F)

Procedure ^a	Predose	Treatment Periods 1 and 2															
		Time point (hours) ^a															
		0	0.25	0.5	1	1.5	2	2.5	3	4	6	8	12	24 ^b	36 ^b	48 ^b	
12-lead electrocardiogram	X						X ^c			X		X	X	X	X	X	
Vital signs	X						X ^c			X		X	X	X	X	X	
Treatment administration 2-hour IV gepotidacin infusion ^d		X															
Blood collection for pharmacokinetics	X		X	X	X	X	X	X	X	X	X	X	X	X	X	X	

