Urine collection for pharmacokinetics ^e	X	X										X	X	X	X	X	
Dialysate collection for pharmacokinetics ^f	X	X		X		X		X									

^a When coinciding with safety and/or pharmacokinetic assessments, electrocardiograms, vital signs, and pharmacokinetic blood collections should be performed in said order.

^b The 24-, 36-, and 48-hour postdose time points correspond to time points on Day 2 and 3, respectively.

^c Performed post infusion.

^d Subjects in Group F will participate in 2 treatment periods, with dosing in these periods separated by a washout period of at least 7 days. Subjects in Group F will enter the clinic at Check-in (Day -1, Period 1 and Day 7, Period 2) before each study drug administration (Day 1, Period 1 and Day 8, Period 2). On Day 1 (Period 1) and Day 8 (Period 2), subjects in Group F will receive a single dose of study drug as follows: gepotidacin 750 mg administered as a 2-hour IV infusion starting approximately 2 hours before initiation of the last hemodialysis session of the week (Period 1) and gepotidacin 750 mg administered as a 2-hour IV infusion starting within 2 hours after completion of the last hemodialysis session of the week (Period 2). Subjects in Group F will be discharged from the clinic on Day 10, Period 2.

^e It should be noted that subjects in Group F may not be able to produce urine samples due to their medical condition. All sampling times are relative to the start of the infusion.

^f Dialysate fluid will be collected on Day 1 after dosing (Period 1 only) over each 1-hour collection interval of the hemodialysis session.

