## Safety and PK Assessments (Group F)

Procedure a	Predose	Treatment Periods 1 and 2 Time point (hours) a														
		0	0.25	0.5	1	1.5	2	2.5	3	4	6	8	12	24 b	36 b	48 b
12-lead electrocardiogram	X						X c			X		X	X	X	X	X
Vital signs	X						X c			X		X	X	X	X	X
Treatment administration 2-hour IV gepotidacin infusion d		X														
Blood collection for pharmacokinetics	X		X	X	X	X	X	X	X	X	X	X	X	X	X	X
Urine collection for pharmacokinetics e	X	X										X	X	X	X	X
Dialysate collection for pharmacokinetics f	X	X		X		X		X								

a When coinciding with safety and/or pharmacokinetic assessments, electrocardiograms, vital signs, and pharmacokinetic blood collections should be performed in said order.

b The 24-, 36-, and 48-hour postdose time points correspond to time points on Day 2 and 3, respectively.

c Performed post infusion.

d Subjects in Group F will participate in 2 treatment periods, with dosing in these periods separated by a washout period of at least 7 days. Subjects in Group F will enter the clinic at Check-in (Day -1, Period 1 and Day 7, Period 2) before each study drug administration (Day 1, Period 1 and Day 8, Period 2). On Day 1 (Period 1) and Day 8 (Period 2), subjects in Group F will receive a single dose of study drug as follows: gepotidacin 750 mg administered as a 2-hour IV infusion starting approximately 2 hours before initiation of the last hemodialysis session of the week (Period 1) and gepotidacin 750 mg administered as a 2-hour IV infusion starting within 2 hours after completion of the last hemodialysis session of the week (Period 2). Subjects in Group F will be discharged from the clinic on Day 10, Period 2.

e It should be noted that subjects in Group F may not be able to produce urine samples due to their medical condition. All sampling times are relative to the start of the infusion.

f Dialysate fluid will be collected on Day 1 after dosing (Period 1 only) over each 1-hour collection interval of the hemodialysis session.

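### Group F has no scheduled ECG or vital signs during the infusion, its post-infusion ECG has no time window, and the timing rules around 2 h and 4 h conflict

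*Protocol*

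**What the plan says.** Protocol section 4.6.1 reports that 1000 mg and 1800 mg infused over 2 hours prolonged ΔΔQTcF by an amount "of 12 msec to 22 msec". On the time course it says: "The QT prolongation evolved during the infusion and was quickly reversed over 2 hours after the end of the infusion". The mitigation it offers is close monitoring and stopping criteria.

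Table 3 (section 7.1) schedules ECG and vital signs for Groups A to E at predose, 1.5, 2, 4, 8, 12, 24, 36 and 48 h. Table 5 schedules them for Group F, in both periods, at predose, 2, 4, 8, 12, 24, 36 and 48 h. Footnote c on the 2 h mark reads "Performed post infusion". PK blood is still drawn at 1.5 h in Group F. The SAP (section 9.1.1) reproduces both schedules unchanged.

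Three rules bear on timing. Section 7 and Table 5 footnote a put the ECG first, then vital signs, then blood; section 7 adds that the blood draw should fall at the exact nominal time. Table 4 footnote a wants assessments other than PK samples done before dialysis on dialysis days. Section 4.2 starts the Period 1 infusion about 2 hours before dialysis.

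Section 5.4.2 withdraws a subject with QTcF above 500 msec or a QTc change above 60 msec. SAP Tables 2.7 and 2.8 summarise the maximum post-dose QTc and the maximum change from baseline.

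**The concern.** The protocol describes a QT effect that builds while the drug runs and fades fast afterwards. Yet the group on hemodialysis is the only one with no scheduled on-infusion ECG or vital signs, and nothing explains why. PK sampling in Group F keeps the 1.5 h time, so access to the subject is not the obstacle.

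Two things are at stake. First, no scheduled ECG in Group F can show that a section 5.4.2 criterion has been met before the infusion ends. Second, comparing safety between normal subjects and subjects with end-stage renal disease is a secondary objective (section 3), and a maximum QTc taken over different time points is not the same quantity in each group.

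**Working it through.** The plan gives no figure to reproduce here. The check compares the schedules and then asks how much the missing window matters.

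**Schedules.** Post-dose ECG times up to 48 h:

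- Groups A to E: 1.5, 2, 4, 8, 12, 24, 36, 48 h = 8, of which 1 falls after the start and before the planned end of infusion.
- Group F, per period: 2, 4, 8, 12, 24, 36, 48 h = 7, of which 0 fall during the infusion. Over two periods: 2 × 7 = 14.

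The protocol and SAP tables agree, and footnote c is specific to Group F, so this is not a text-extraction artefact.

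**Conflict at 2 h.** The infusion is planned to end at nominal 2 h, and PK blood is due at 2 h. The ordering rule puts the ECG before a draw made at exactly 2 h, so before the planned end of infusion. Footnote c puts it after the infusion. Both cannot be met if the infusion and the draw run to time.

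**Conflict at 4 h, Period 1.** Dialysis starts about 2 h after the start of infusion. Inclusion criterion 5 refers to sessions of 3 to 4 hours, so dialysis runs from about 2 h to 2 + 3 = 5 h or 2 + 4 = 6 h. The 4 h ECG falls inside it, against Table 4 footnote a.

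**Does the 2 h ECG catch the peak?** For illustration, fit a one-compartment model to the simulated values in Table 1. Assumptions: AUC(0-t) stands for AUC(0-∞), QT effect follows concentration without delay, and no dialysis clearance (the documents give none). The infusion rate is 750/2 = 375 mg/h and CL = 750/AUC, so:

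- Css = 375/CL = AUC/2
- k = −ln(1 − Cmax/Css)/2
- C(1.5) = Css × (1 − e^(−1.5k))
- Delay after the end of infusion at which concentration is back to the 1.5 h level: ln(Cmax/C(1.5))/k

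Normal renal function: Css = 17.5/2 = 8.75; k = −ln(1 − 5.65/8.75)/2 = 0.519 per h; C(1.5) = 4.73, and 4.73/5.65 = 84%; delay = 0.342 h = 20.5 min.

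| Table 1 column | Cmax | AUC(0-t) | k (per h) | C(1.5)/Cmax | Break-even delay |
|---|---|---|---|---|---|
| Normal | 5.65 | 17.5 | 0.519 | 84% | 21 min |
| Moderate | 7.29 | 25.8 | 0.416 | 82% | 28 min |
| Severe | 7.93 | 28.9 | 0.398 | 82% | 30 min |

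Across the three columns, an ECG delayed by 5, 15 or 30 min is taken at 96–97%, 88–91% or 77–82% of the peak concentration. If instead the QT effect falls linearly to zero over 2 h, a peak of 12 to 22 msec reads 12 × (1 − 15/120) = 10.5 to 22 × (1 − 15/120) = 19.25 msec at 15 min, and 9.0 to 16.5 msec at 30 min.

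**Context.** Criterion 17 of section 5.2 excludes a subject when a "subject with renal impairment has a baseline QTcF of >480 msec". Entry at 480 msec is therefore possible, which leaves 500 − 480 = 20 msec to the withdrawal limit. The same entry limit applies to Groups B, C and E, which do have an on-infusion ECG.

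**The case against.** The strongest reply is that the missing reading is not the important one. If the effect builds through the infusion, its maximum is at about the end. Group F has an ECG there, and the 1.5 h reading comes earlier, at about 82–84% of peak concentration. In Period 1 the before-dialysis rule, combined with dialysis starting at about 2 h, pushes that ECG to be prompt. This stands, and it defeats the inference a reader might draw that Group F has no reading at the peak. What remains is that promptness is not specified. In Period 2 dialysis is already over, so not even that indirect limit applies.

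A reader might also infer that Group F's maximum QTc is biased low against every other group. The documents do not support that. Group F has two periods, hence 14 treatment-period readings against 8 if maxima are taken over both. The SAP defines baseline per period (section 9.3.2.1) but does not say how Tables 2.7 and 2.8 treat periods. Part 1 and Part 2 outputs are separate (SAP section 9.3.1), so Group F's tabled comparators are only Groups D and E, either of which may not be enrolled. The direction of any bias is open; the lack of a common basis is not.

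Nor is it right that the QTc criteria cannot be triggered during a Group F infusion. Section 5.4.2 recognises ECGs outside the schedule, section 7.3.5 refers to additional QTc readings, and sections 7 and 7.3 allow time points to be added. The statement is limited to scheduled ECGs.

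Finally, Group F opens only after review of Part 1, where Group C has 1.5 h ECGs, and safety is not tested inferentially (section 9.4.2.1). Both points reduce the stakes. Neither explains the difference in schedule.

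**Conclusion.** The point holds in a limited form. Group F has 0 scheduled on-infusion ECG and vital-sign assessments against 1 in the other groups, with no reason given. The one reading near the expected peak has no window, in a setting where about 21 to 30 minutes' delay takes it below the 1.5 h level. That range rests on the one-compartment model, on Table 1 populations that do not include hemodialysis, and on no hysteresis; dialysis in Period 1 could shorten it. The timing rules at 2 h, and at 4 h in Period 1, contradict each other whatever the model.

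Tables 2.7 and 2.8 are therefore not like for like between Group F and Groups D and E: 7 against 8 post-dose times per period. The 20 msec of headroom set against a mean effect of 12 to 22 msec at higher doses shows why timing matters. It is not evidence that an event would be missed, and Group F's dose may be reduced (sections 4.1 and 6.3). The primary PK analysis is unaffected. This should be settled before Group F is enrolled.

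**What to change.** The sponsor should reconcile Tables 3, 4 and 5, and the SAP copies, with section 4.6.1. Either align Group F's on-infusion assessments with those of the other groups or state why they differ. Which schedule is appropriate is a clinical decision for the sponsor. In either case, give a window for the post-infusion ECG, and say which rule governs at 2 h and at 4 h in Period 1.

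If the schedules stay different, amend the programming notes for SAP Tables 2.7 and 2.8. Compute between-group maxima on the time points common to the groups compared, show Group F separately by period, and footnote the missing on-infusion reading. The 2 h label is common to all groups, but the timing behind it is not until the window is set.

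The cost is small. Alignment would add one ECG and one set of vital signs per period in 4 to 8 subjects, that is 2 × 4 = 8 to 2 × 8 = 16 of each, in subjects already confined and being sampled, plus a table edit. The alternative is a written justification and slight extra programming.
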